1.2 Study Design Configuration

This study is designed as a prospective, interventional, single arm, open label study.

2 Centers

This study is a multi-center study. It is expected that 150 subjects will be enrolled to the study in up to 30 sites.

3 Study Objectives

- To demonstrate efficacy of BlueWind RENOVA iStim™ System therapy in female patients with UUI.
- To demonstrate the safety of BlueWind RENOVA iStim™ System therapy in female patients with UUI.

4 Treatment Groups

This study is a single arm study. All subjects will receive active RENOVA iStim™ System treatment for the duration of the study.

5 Study Schedule

Table 1 - Study Schedule of Events

#	Section name	Enrollment and Screening	Implantation (6 ± 4 weeks)	Activation (4 ± 2 weeks)	FU 1m (±2 weeks)	FU 3m (±2 weeks)	FU 6m (±4 weeks)	FU 9m (±4 weeks)	FU 12m (±4 weeks)
	Visit	1	2	3	4	5	6	7	8
1.	Informed consent form	Х							
2.	Patient Demographics	Х							
3.	Inc/Exc criteria	Х							
4.	Medical History	Х							
5.	Physical & Neurological Exam (including vital signs) *partial physical examination	Х	X*	Х*	X*	X*	X*	X*	Х
6.	Urinalysis	Х		Х	Х	Х	Х	Х	Х
7.	Urine culture (at baseline, *and then pending urinalysis results)	Х		*	*	*	*	*	*
8.	Urine/blood pregnancy test (if bearing potential)	Х							
9.	Post Void Residual	Х							
10.	Blood – chemistry (Creatinine levels; GFR, and HbA1C)	Х					Х		Х
11.	Medications	Х	Х	Х	Х	Χ	Х	Χ	Х
12.	Quality of Life Questionnaire	Х					Х		Х
13.	MESA incontinence questionnaire	Х							
14.	PHQ-15	Х							
15.	PGI-I						Х		Х
16.	BSW						Х		Х
17.	Voiding Diary	X (7-days)			X (3-days)	X (3-days)	X (7-days)	X (3-days)	X (7-days)
18.	Usability/patient satisfaction questions		Х	Х	Х	Х			
19.	Parameter Setting			Х	Х	Х	Х	Х	Х
20.	Leg circumference measurements	Х	Х	X	Х	Х	Х	Х	Х
21.	Patient Training on wearable unit			X					
22.	Adverse Event		Х	Х	Х	Χ	Χ	Χ	Х
23.	Study completion/discontinuation form								Х

Document ID	Revision / Date	Page
G02-CLP-0009	Rev. 06 / 18 May 2022	9 of 26

Table 2 - Study Schedule of Events – Long Term Follow-up

#	Section name	Long Term FU Consent Visit	FU 18m (±6 weeks)	FU 24m (±6 weeks)	FU 30m (±6 weeks)	FU 36m (±6 weeks)
	Visit		9	10	11	12
1.	Informed consent form	Х				
2.	Inc/Exc criteria (verify new criteria – if exited study at 12m FU)	Х				
3.	New medical history since 12m FU visit	X				
4.	Physical & Neurological Exam (including vital signs) *partial physical examination †if in clinic	Х	X*†	X*	X*†	Х*
5.	Urinalysis †if in clinic	Х	Χ [†]	х	Χ [†]	Х
6.	Urine culture *pending urinalysis results +if in clinic	X*	X* [†]	X*	X* [†]	Х*
7.	Urine/blood pregnancy test (if bearing potential)	Х				
8.	Medications	Х	Х	Х	Х	Х
9.	Quality of Life Questionnaire			Х		Х
10.	PGI-I			Х		Х
11.	BSW			Х		Х
12.	Usage information collection	Х	Х	Х	Х	Х
13.	Voiding Diary (3-days)	Х	Х	Х	Х	Х
14.	Voiding Diary (UUI for ~4 weeks)					
15.	Usability/patient satisfaction questions		Х		Х	
16.	Parameter Setting †if in clinic		Χ [†]	Х	X [†]	Х
17.	Leg circumference measurements	Х				
18.	Patient Training on wearable unit	Х				
19.	Adverse Event	Х	Х	Х	Х	Х
20.	Study completion/discontinuation form					Х

Document ID	Revision / Date	Page
G02-CLP-0009	Rev. 06 / 18 May 2022	10 of 26

6 Analysis Populations

6.1 Safety and Efficacy Analysis Population – Intent To Treat (ITT)

The safety and effectiveness endpoints will be evaluated under principles of Intent to Treat (ITT). The analysis set will consist of all subjects for whom the implantation of the BlueWind RENOVA iStim[™] system was attempted. Specifically, the analysis set will consist of all subjects for whom skin incision time was not missing.

6.1.1 Per Protocol Population (PP)

The per protocol analysis set (PP) will be a subset of ITT subjects with observed data on the endpoint analyzed. Excluded will be subjects with major protocol violations, where "major" is defined has having the potential to meaningfully affect outcome. A list of major protocol violations, as assessed by qualified personnel who is masked to patient outcomes will be provided by the Sponsor prior to database lock. Subjects with a major protocol violation will be excluded globally in the PP population.

Also excluded from per visit analyses will be subjects with less than 50% compliance (i.e. those who received treatment on fewer than 50% of days during which they were eligible for therapy delivery) for the period prior to the visit. These will be local exclusions for the timepoint the subject is considered non-compliant.

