10.4 Medication Usage

If used, patients should be on stable dose of OAB related medication (i.e. antimuscarinics and/or beta-3 adrenergic agonists for at least 3 months prior to baseline and agree to remain on stable medication consumption until the 12-month follow-up visit.

If used, patients should be on a stable dose of tricyclic antidepressants, Selective Serotonin Reuptake Inhibitors (SSRI) and Serotonin-Norepinephrine Reuptake Inhibitors (SNRI)) for at least 3 months prior to baseline.

Type and dosage of OAB related medications as well as any change in consumption during the study will be recorded in the CRF. All other medication consumption will be recorded in the CRF during the baseline visit and tracked 3 months back.

Number	Revision / Date	Page
G02-CLP-0002_US	Rev. 08 / 27 July 2021	31 of 75

Patients should avoid any OAB intervention (such as PTNS, SNM, or other neuromodulation treatments, Botox injections, surgical procedures, etc.) that may have an effect on overall study results throughout the 36 months follow-up period.

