1.1 General

This is a prospective, single arm, multi-center, open label study whose primary objective is to assess the safety and efficacy of the BlueWind RENOVA iStim™ system for the treatment of UUI. The trial's secondary objectives are to evaluate device performance, durability of effect and patient reported outcomes (PROs) such as quality of life (QoL). This SAP is applicable to the following protocol versions:

Country	Document No.	Version/Date
Belgium	G02-CLP-002_BE	Rev. 06 / 27 Jul 2021
Netherlands	G02-CLP-002_NL	Rev. 06 / 27 Jul 2021
United Kingdom	G02-CLP-002_UK	Rev. 06 / 27 Jul 2021
United States	G02-CLP-002_US	Rev. 06 / 27 Jul 2021

Once all patients complete six months of follow-up, a complete data analysis will be performed and submitted to relevant regulatory bodies, with a 12-month update and endpoint evaluation performed and submitted at study completion.

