12.6 Efficacy

12.6.1 Primary Efficacy Analysis

The following primary efficacy analyses will be carried out using the ITT population with multiple imputation as described in Section 7.1. The primary efficacy analysis will test the null hypothesis that the response probability on the primary efficacy endpoint is less than or equal to 50%. The alternative hypothesis for the primary analysis is that patients receiving the treatment have above 50% probability to achieve clinical improvement, as follows:

$$H_0: \pi_{Renova} \leq \pi_{PG}$$

$$H_1: \Pi_{Renova} > \Pi_{PG}$$

where π_{Renova} is the proportion of subjects meeting the pre-defined success criterion with RENOVA therapy (\geq 50% improvement in average number of urge related incontinence episodes, measured by a 7-day Patient Voiding Diary at 6 months post system activation), and π_{PG} is the prespecified performance goal (PG) of 50%.

Although sample size was conservatively calculated under an Exact Binomial test, the hypothesis will be tested by performing the logistic regression on each imputed dataset as described in Section 7.1. Then SAS PROC MIANALYZE procedure will be used to calculate the combined confidence interval and the corresponding p-value.

We will declare success on this endpoint if the lower limit of the confidence interval is above 50%.

Document ID	Revision / Date	Page
G02-CLP-0009	Rev. 06 / 18 May 2022	21 of 26

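### The per-protocol rule for major violations has no date limit, so a violation after month 6 can remove a valid month-6 result from the supportive analysis (minor)

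*SAP*

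**What the plan says.** SAP 6.1.1 builds the PP set from ITT women with observed data on the endpoint being analysed, so membership already varies by endpoint. Two further exclusions apply.

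- **Major protocol violations.** A violation is major if it "is defined has having the potential to meaningfully affect outcome"; no visit or endpoint is named. A list, "as assessed by qualified personnel who is masked to patient outcomes will be provided by the Sponsor prior to database lock", identifies these women. Their exclusion covers every time point: "Subjects with a major protocol violation will be excluded globally in the PP population".
- **Treatment on fewer than 50% of eligible days.** This is judged over the period before each visit and removes the woman only there: "These will be local exclusions for the timepoint the subject is considered non-compliant".

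Protocol 13.2.2 also excludes major violators and poor compliers but does not say over which time points.

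On timing, SAP 1.1 says: "Once all patients complete six months of follow-up, a complete data analysis will be performed and submitted to relevant regulatory bodies". A 12-month update follows. On role, SAP 12.6.1 says: "The following primary efficacy analyses will be carried out using the ITT population with multiple imputation as described in Section 7.1". Protocol 13.5.1 calls the PP analysis of the primary endpoint supportive. SAP 12.6.2 repeats the primary analysis on PP and also analyses the three secondary endpoints there, two of them at month 6.

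**The concern.** The reason for excluding a major violator is that the violation may have altered her outcome. A violation after the month-6 diary cannot have altered that diary. Deleting the result therefore fails the SAP's own rationale and makes membership of the month-6 analysis depend on what happened later.

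Such violations can occur. Protocol 10.4 tells women to avoid other OAB interventions "that may have an effect on overall study results throughout the 36 months follow-up period". Because the month-6 analysis waits for the last woman, those enrolled early have a long stretch of later follow-up in which they can be excluded, and those enrolled last have almost none.

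At stake is how far the month-6 PP rates can be trusted as robustness evidence in a single-arm trial judged against fixed performance goals. The primary decision is not at stake.

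**Working it through.** **1. The plan's own figures.** The documents give no PP response rate and no expected number of violators. The related figure is the primary sample size: a one-sided exact binomial test of 65% against 50% at 0.025 (Protocol 13.4, SAP 9). At 90% power the smallest sample size is 114, with success at 68 or more responders, actual alpha 0.0244 and power 0.9015. This reproduces the stated 114, and 114/0.85 = 134.1 matches the stated 134. (SAP 9 prints 80% power beside 114, but 80% needs only 90 women. That is a separate point.) The check below takes the 65% response rate and 15% attrition from this calculation.

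**2. Side-by-side reading.** The compliance rule is tied to the period before a visit and acts at that visit. The violation rule is tied to no period and acts at all visits. Nothing elsewhere in either document limits it to violations before the endpoint.

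**3. Opportunity.** Protocol 10.9 gives about 18 months of enrollment. If accrual were even, (18 − 6)/18 = 67% of women would have passed month 12 when the last woman reached month 6. This is only indicative: Protocol 10.2.1 pauses implantation for a safety review of up to 30 subjects, so accrual was not planned to be even.

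**4. Effect on the rate.** Let p be the month-6 response rate before late exclusions, f the share of women removed for a violation after month 6, and q the response rate among those removed. Then

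PP rate = (p − f·q)/(1 − f), and shift = f·(p − q)/(1 − f).

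The sign depends only on whether q is below or above p. With p = 65% (documents), and f and q assumed:

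| q (responders among removed) | f = 2% | f = 5% | f = 10% |
|---|---|---|---|
| 0% | 66.3% | 68.4% | 72.2% |
| 25% | 65.8% | 67.1% | 69.4% |
| 50% | 65.3% | 65.8% | 66.7% |
| 65% | 65.0% | 65.0% | 65.0% |
| 80% | 64.7% | 64.2% | 63.3% |
| 100% | 64.3% | 63.2% | 61.1% |

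Example: f = 5%, q = 0 gives 0.65/0.95 = 68.4%; f = 5%, q = 100% gives (0.65 − 0.05)/0.95 = 63.2%.

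**5. The same in whole women.** 150 × 0.85 = 127.5, taken as 127 evaluable, with 83 responders (65.4%). Remove six women:

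- six non-responders: 83/121 = 68.6%
- four responders and two non-responders: 79/121 = 65.3%
- six responders: 77/121 = 63.6%

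An exact one-sided test at 0.025 against 50% needs 72 of 121. All three cases clear it, so at the planned response rate the rule moves the supportive estimate without changing its conclusion.

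**6. Effect on the primary result.** None. ITT membership depends on an attempted implantation, not on violations.

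**The case against.** The strongest reply is that no document classes a later OAB intervention as a major violation. Need for other third-line therapy appears instead as a failure: a discontinuation reason in Protocol 10.8.1 and a missing-data category in SAP 7.1. A woman who leaves on that route after month 6, with her diary already observed, stays in the month-6 PP set unless the assessor also lists a violation. This stands, and it is why upward bias cannot be asserted.

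Changes in OAB medication are a weaker example still. Stable medication is asked for up to month 12, but Protocol 10.4.2 and 11.4.1 say that medically required changes are recorded and the woman continues as planned, and SAP 12.8 analyses such changes by subgroup. This also stands.

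A masked assessor might decline to list an event after month 6 as major for month 6. That is possible, but the definition names no endpoint and the exclusion covers all time points, so the text points the other way. Masking limits discretion; it does not prevent selection through the event itself.

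Global exclusion may also be deliberate strictness, and visit-specific exclusion suits compliance because compliance is measured visit by visit. The two rules need not be contradictory. Even so, strictness gives no reason to discard a result that predates the violation.

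Finally, PP is supportive. That stands and sets the severity.

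**Conclusion.** The defect is real but minor. As written, SAP 6.1.1 lets a violation after month 6 delete a valid month-6 result, and no other text corrects this. At a 65% response with 5% of women removed, the month-6 PP rate could move from 3.4 points up (68.4%) to 1.8 points down (63.2%). The 5% and the response rate among those removed are assumptions.

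Two stronger readings are tempting and not supported.

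- **That the rule inflates the month-6 PP rate.** This is plausible if late violators are mainly non-responders, for example women who take another OAB intervention and are listed as major violators for it. The plan's own failure categories make that link credible, but the documents give neither the classification nor any rate. A scenario that gives non-responders several times the violation rate of responders produces an upward shift by construction.
- **That the month-6 PP set will change between the 6-month submission and the 12-month update.** SAP 1.1 promises an update and endpoint evaluation; it does not say that the month-6 PP analysis is rerun with a revised violation list.

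**What to change.** In SAP 6.1.1, replace the global-exclusion sentence with wording such as:

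> A major protocol violation excludes a subject from PP for each endpoint whose diary or questionnaire was completed on or after the date of the violation. A violation of the eligibility criteria excludes the subject from PP at all time points.

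Add the violation date to the list prepared by the masked assessor before database lock.

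The cost is one sentence and one data column. PP membership would differ by time point, as it already does for compliance and observed data. If late violators are mainly non-responders, the month-6 PP rate may be slightly less favourable. The ITT analysis, alpha, sample size and trial conduct do not change.

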6.1.2 One-month Responders (OR1)

The one-month responder analysis set (OR1) will be a subset of ITT of subjects who are classified responders in urinary incontinence at one month, defined as \geq 50% reduction from baseline to one-month in average number of urgency-related leaks/day (urinary incontinence).

Percent reduction is defined as it is for the primary endpoint (see section 7.2, below) as related to the 3-day diary collected at the one-month follow-up. For the purposes of the OR1 population, all available diary data will be used (including partial data).

7 Handling of missing data

7.1 ITT population

Treatment of missing values:

- Subjects missing data "not in random" will be imputed as "failure" on dichotomous endpoints.
- "Failures" (not MAR) include:
 - Subject leaves the study due to related AE
 - Device explant
 - o Lack of effect that results in significant increase of UUI medication
 - Need for other 3rd line therapies for the management of UUI

Document ID	Revision / Date	Page
G02-CLP-0009	Rev. 06 / 18 May 2022	11 of 26

- Baseline values will not be imputed
- Missing values in ITT not due to "failure" will be imputed using multiple imputation (MI).

Multiple imputation will be applied to the primary and three secondary endpoints. The 'additional endpoint' analyses will not use multiple imputation. The imputation procedure will be performed on the continuous outcomes (e.g. number of incontinence episodes). Based on the imputed continuous outcome, the response will be defined accordingly for each endpoint.

The hypotheses will be tested by performing the logistic regression on each imputed dataset. Then SAS PROC MIANALYZE procedure will be used to calculate the combined confidence interval and the corresponding p-value. The evaluation on each endpoint will be successful if the lower limit of the confidence interval is above 50%. In addition, the primary analysis will present the observed frequency of responders and descriptive statistics of response rates over all imputed datasets.

Fifty (50) imputed datasets will be created (the seed is set to 123456).

The imputation will be done using covariates: Age, BMI, average number of urgency leaks, average number of urgent voids, HRQL score and OAB duration at baseline. This list might be reduced if the model fails to converge.

Because MI assumes missing at random (MAR), sensitivity analyses (i.e. tipping point) described below, will be conducted to test the effects of other patterns of missingness.

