8.4 Additional Efficacy Endpoints

The following additional efficacy endpoints will be assessed based on the data summarized in the data management reports:

- Patient Global Impression of Improvement (PGI-I) score
- Treatment Benefit, Satisfaction, and Willingness to Continue (BSW)
- Improvement in OABq (HRQL (and its subscales) and symptoms severity)
- Changes in the following OAB symptoms as measured by voiding diary 6 and 12-months post system activation compared to baseline:
 - o Reduction in the average number of severe/large urgency related incontinence episodes
 - o Reduction in the number of micturition episodes.
 - o Reduction in the number of urgency related incontinence episodes.
 - Reduction in degree of urgency prior to void on Patient Perception of Intensity of Urgency Scale (PPIUS) from 0-4.
 - o Reduction in severity of incontinence episodes (amount leaked).
- Proportion of dry subjects following treatment with the RENOVA iStim System as measured by 3
 consecutive days of a patient voiding diary.
- Assessment of fecal incontinence symptoms in patients suffering from mixed fecal and urine incontinence.
- Device usage
- Patient compliance with treatment through 6-months

Instructions for Diary calculation are as detailed in the appendix to the SAP.

9 Sample Size Considerations

The sample size for the primary endpoint was calculated using PASS 2015 software by a one-sided exact test for a single binomial population, under the following assumptions:

Document ID	Revision / Date	Page
G02-CLP-0009	Rev. 06 / 18 May 2022	15 of 26

- Significance level = 0.025 (one-sided)
- Power ≥ 80%
- Assumed treatment success rate at 6 months = 65%
- Prespecified performance goal = 50%.

Given these assumptions, 114 evaluable subjects are required. A total of 134 enrolled subjects, accounting for 15% attrition, is sufficient to evaluate the primary endpoint. However, this sample size is not adequate to evaluate all secondary objectives with sufficient power – specifically the following important secondary objective:

To demonstrate the proportion of responders at 6 months post system activation, defined by ≥50% improvement in the average number of moderate-severe urgency episodes PPIUS degree 3,4 or <8 voids/day, is greater than 45%.

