12.6.3 Additional Efficacy Analysis

The additional efficacy endpoints will be assessed descriptively on the ITT, PP and OR1 populations. Descriptive statistics will be provided for diary parameters collected within the Axiom data management report and will include the following by visit for each diary period available:

- Patient Global Impression of Improvement (PGI-I) score
- Treatment Benefit, Satisfaction, and Willingness to Continue (BSW)
- Improvement in OABq (HRQL (and its subscales) and symptoms severity)
- Changes in the following OAB symptoms as measured by voiding diary 6 and 12-months post system activation compared to baseline:
- Reduction in the average number of severe/large urgency related incontinence episodes
- Reduction in the number of micturition episodes.
- Reduction in the number of nocturia episodes.

Document ID	Revision / Date	Page
G02-CLP-0009	Rev. 06 / 18 May 2022	22 of 26

- Reduction in the number of urgency related incontinence episodes.
- Reduction in degree of urgency prior to void on Patient Perception of Intensity of Urgency Scale (PPIUS) from 0-4.
- Reduction in severity of incontinence episodes (amount leaked).
- Proportion of dry subjects following treatment with the RENOVA iStim System as measured by 3
 consecutive days of a patient voiding diary.
- Assessment of fecal incontinence symptoms in patients suffering from mixed fecal and urine incontinence.
- Device usage
- Patient compliance with treatment through 6-months
- Descriptive statistics of percent compliance with treatment will be presented by center and visit.

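### ITT mean changes on the additional endpoints omit women whose data are missing through a failure event, so they will tend to look too favourable

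*SAP*

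**What the plan says.** SAP 7.1 lists four kinds of failure that it regards as not missing at random: leaving the study because of a related AE, device explant, lack of effect leading to a significant rise in UUI medication, and need for another third-line therapy. For these, "Subjects missing data 'not in random' will be imputed as 'failure' on dichotomous endpoints". Other missing ITT values go to multiple imputation (MI), but its scope is limited: "Multiple imputation will be applied to the primary and three secondary endpoints". The next sentence is "The 'additional endpoint' analyses will not use multiple imputation".

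SAP 12.6.3 then says: "The additional efficacy endpoints will be assessed descriptively on the ITT, PP and OR1 populations". For diary parameters, the descriptive statistics "will include the following by visit for each diary period available". The list contains continuous measures such as "Reduction in the number of urgency related incontinence episodes", "Reduction in the number of micturition episodes" and "Improvement in OABq (HRQL (and its subscales) and symptoms severity", together with large leaks and PPIUS degree. No value is set for a continuous measure that is missing because of a failure event. The tipping-point analysis in SAP 12.7 concerns the primary outcome only.

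The protocol is broader. Section 13.3 prescribes MI for ITT effectiveness endpoints, and 13.2.1 prescribes it for ITT values missing for reasons other than failure. Neither excepts the additional endpoints.

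**The concern.** The month-6 leak count feeds two ITT results. In the response rate, a woman missing for a failure reason is scored as a non-responder. In the mean leak reduction she is not counted at all. Both results carry the ITT label, but they treat the same woman differently.

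The omission is selective. The plan itself says that these women's data are missing for reasons tied to harm or lack of effect, so leaving them out will generally raise the mean improvement. At stake is the credibility of the mean changes in leaks, voids, urgency and quality of life that will be read beside the response rate. The formal conclusion of the trial is not at stake.

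**Working it through.** **The plan's own figures.** The plan states no mean change, SD or failure share, so there is no figure on this point to reproduce. The nearest is the 15% attrition in SAP section 9. For the secondary endpoint that drives the sample size, 89/0.85 = 104.7, or 105, and 105/0.70 = 150. The stated total follows. The 15% is total attrition for any reason (0.15 × 150 = 22.5 women), not the failure share.

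**Treatment of one woman missing at month 6 because of explant**

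| ITT result | Rule | Her contribution |
|---|---|---|
| Leak response rate | SAP 7.1, dichotomous failure rule | Failure |
| Mean change in leaks | SAP 7.1 and 12.6.3: no MI, no failure value | None |

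**Formula.** Let f be the share of ITT women missing for a failure reason, m the mean change among the rest, and k the change in the missing women as a fraction of m. To isolate this effect, suppose that there is no other missingness.

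- Full mean = (1−f)m + f·k·m
- Observed mean / full mean = 1/(1 − f(1−k))
- With no change in the missing women (k = 0), the ratio is 1/(1−f).

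**Inputs for f (all assumptions for this trial).** Protocol 7.2 reports that 36 pilot patients were implanted and 34 were in the performance analysis. One device was explanted for suspected infection and one patient withdrew for personal reasons. Only the explant is a failure event, which gives f = 1/36. The values 5% and 10% are illustrative.

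| f | Observed mean too high by, k = 0 | Same, k = 0.5 |
|---|---|---|
| 1/36 | 36/35 − 1 = 2.9% | 72/71 − 1 = 1.4% |
| 5% | 1/0.95 − 1 = 5.3% | 1/0.975 − 1 = 2.6% |
| 10% | 1/0.90 − 1 = 11.1% | 1/0.95 − 1 = 5.3% |

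For scale, at f = 10% and k = 0, an observed fall of 2.5 leaks/day corresponds to 2.5 × 0.90 = 2.25 over all ITT women, and a 20-point HRQL gain to 18. If the missing women improved as much as the others (k = 1), there is no shift.

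**Contrast with the response rate.** If 65% of observed women respond (the rate assumed in SAP section 9), scoring the failure share as non-responders gives 0.65 × 0.95 = 61.75% at f = 5% and 0.65 × 0.90 = 58.5% at f = 10%. The failure rule lowers the response rate, but has no counterpart for the means.

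**Where MI already exists.** From the endpoints in SAP 8.2 and 8.3, MI covers leaks at months 6 and 12, large leaks at month 12, and HRQL at month 6. Voids and urgent episodes are imputed at month 6 only, for women with at least 8 voids/day and at least 9 urgent episodes at baseline, who are expected to be 70% of those enrolled. PPIUS degree, the OAB-q subscales and symptom severity are not imputed as outcomes.

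**The case against.** The strongest reply is that these endpoints are descriptive, without formal tests, and that observed-case description is a choice made in advance. The two results that matter most, leak response and the 10-point HRQL gain, already have failure scoring plus MI. That stands, and it limits the point to how the means are presented.

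Several stronger readings are tempting, but the documents do not support them:

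- **That explanted or exited women disappear, or that the means are completer-only.** The summary is by visit, so a woman contributes wherever she has data, and nothing discards data collected after explant or third-line therapy. Numbers of subjects, accountability by visit and a dropout listing are all required (SAP sections 12 and 12.1), so the denominator is disclosed.
- **That all missing women did badly.** The plan presumes this only for the four failure categories. Withdrawal for personal reasons and visits missed through COVID-19 do not carry that label.
- **That the inflation reaches 18%.** That is 1/0.85 − 1 = 17.6%, which treats all planned attrition as failure.
- **That the means cannot be reconciled with the response rate.** SAP 7.1 also requires the observed frequency of responders, which gives a comparable observed-case rate.
- **That no failure rule reaches BSW.** Each BSW domain opens with a yes/no question (protocol Appendix 1), so the dichotomous rule arguably applies, as it does to the dry proportion. PGI-I has seven categories and no rule.

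Observed-only analysis is written out for PP and OR1 (SAP 7.2 and 7.3). For the ITT additional endpoints it is inferred from the exclusion of MI and the reference to available diary periods. No other rule is offered, so the inference is sound.

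**Conclusion.** The point holds for the continuous additional endpoints. As written, ITT means at months 6 and 12 exclude women whose data are missing for reasons that the plan itself calls not missing at random, while the ITT response rate from the same month-6 leak count scores them as failures. The means will tend to be too favourable: by about 3% at the pilot's 1 in 36, 5% at f = 5% and 11% at f = 10%, if these women had no change, and by about half as much if they improved half as much as the others. The pilot share comes from 36 patients with a first-generation device and is only indicative.

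A reader might infer that the trial's success claim is at risk. It is not: the primary and secondary tests use the failure rule and MI, and type I error is unaffected. Separately, protocol 13.3 and SAP 7.1 disagree on whether MI applies to the additional endpoints.

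**What to change.** In SAP 7.1 and 12.6.3:

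1. Keep the present ITT summary, label it observed-case, and show n at each visit.
2. Add one ITT sensitivity column at months 6 and 12 for the continuous measures. Set women with data missing because of a SAP 7.1 failure event to no change from baseline. Take other missing values from the existing imputed datasets only where that variable and visit are imputed for all ITT women: leaks at months 6 and 12, large leaks at month 12, HRQL at month 6. Elsewhere leave them missing, with n shown.
3. State that the existing failure rule applies to the dichotomous additional endpoints: dry, and the BSW yes/no items. For PGI-I, count failure-type missing women as not improved.
4. Reconcile protocol 13.3 with SAP 7.1 on the scope of MI.

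The cost is SAP wording, a protocol clarification and some extra programming, since the missing-data rule in the new column differs by measure and visit. The means in that column will be somewhat less favourable. No new data are needed.
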